11.1 Estimated Sample Size

One of the study goals is to identify consistent efficacy trends in the primary and key secondary endpoints. Twenty-five subjects per group will generate 70% power to detect the effect size of 0.6 at the 0.1 two-sided significance level. This sample size will also be sufficient to generate 80% power to detect the effect size of 0.82 at the 0.05 two-sided significance level. Accounting for a 10%-13% drop-out rate, approximately 28 subjects per group were initially planned. No data are available on the CDM1-RS instrument. Based on the preliminary data observed in the AMO-02-MD-2-001 study, the assumed effect sizes look reasonable. The effect size assumptions are partially based on the Clinician VAS total score changes from baseline to end of study (6 points on drug vs. 1 point on placebo with the common standard deviation of 5.8). Based on these and other data, 29 and 22 subjects per group will be sufficient to generate 90% and 80% power at the 0.05 two-sided significance level. Based on these calculations, the suggested sample size of 56 patients total was considered adequate to detect the treatment effect or at least a consistent trend.

A blinded SSRE, based on the observed variance in the primary outcome measure, was performed during the conduct of the study. Based on the blinded SSRE, the planned sample size is sufficient to detect the treatment difference between active and control arms based on the primary endpoint with at least 80% power at the 0.05 two sided significance level. However, the variability of the key secondary endpoint was slightly greater than that originally assumed. Respectively, it was recommended, if operationally feasible, to increase the total sample size to a maximum of 66 subjects.

However, based on the blinded SSRE, the pooled standard deviation of change from baseline for the primary endpoint was 2.64. Assuming this standard deviation and as long as the difference in the primary endpoint mean change from baseline to EOT between drug and control is at least 2.2, the power to detect treatment differences will be 82% if n=25/group.

The details of the SSRE and summary of scenarios and outcomes are outlined in the SAP.

Investigational Medicinal Product: Tideglusib

Protocol No: AMO-02-MD-2-003 AMO Pharma Ltd.

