The model will contain treatment, age group, visit and treatment by visit interaction as fixed effects, baseline CDM1-RS as a covariate.

If the baseline CDM1-RS and/or age group is not significant at the 15% level (i.e., p>=0.15) then a secondary analysis will be conducted with the term(s) removed from the model. Similarly if the p-value for the treatment by visit interaction is not significant at the 15% level, that term will be removed in the secondary analysis and the LS

Date:22FEB2023 Version: Final 2.0 ST/form/010/15 Means and treatment differences under the assumption of a constant treatment effect over time will be estimated.

Normality of the data will be investigated through plots of the residuals. Non-parametric analyses may additionally be performed if the data are found to be sufficiently non-normal. This will include non-parametric analysis of covariance (ANCOVA) (Koch G.G. et al, 1998 and Zink, R. and Koch, G.G., 2012) of the change from baseline to Visit with treatment, baseline CDM1-RS and age group as covariates.

Any data collected after study discontinuation will not contribute to the treatment effect estimate. Only data up to study discontinuation will be used.

Missing Data

Missing data due to early study discontinuations or missed visits are assumed to be missing at random (MAR) and observed data only will be used for the primary analysis. The MMRM accounts for these missing data using a direct likelihood approach.

Sensitivity Analysis

Several sensitivity analyses will be applied to this endpoint:

Sensitivity analysis 1 – Multiple Imputation: Missing at Random (MAR)

At a visit, if a subject has no in-clinic or telehealth assessment data the visit is assumed to be MAR. This assumes that subjects with missing data follow the same trajectory as other subjects in their respective treatment arm that have complete data.

- Intermittent missing data will first be imputed using the MCMC method, appropriate for non-monotonic missing data.
- Data missing after subjects discontinue the study early will be imputed using a regression, appropriate for monotone missingness. At each time point, missing data will be assumed to follow a distribution similar to scores for subjects who are still in the study and randomized to the same treatment group.

The MI method (as described in Section 6.3) will be employed with the following assumptions/steps:

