 regression, appropriate for monotone missingness. At each time point, missing
 data will be assumed to follow a distribution similar to scores for subjects who
 are still in the study and randomized to the same treatment group.

The MI procedure will be employed as described for sensitivity analysis 1. The MMRM will be applied to the multiply imputed data sets, as described above for the primary estimand. The estimates from these models will then be combined using Ruben's (1987) rule and analysed to provide the endpoint estimates and summarized.

Sensitivity analysis 5 – Completers

The MMRM will be applied to all subjects who have completed the study to EOT.

Sensitivity Analysis 6 – Rank Analysis

The change from baseline in CDM1-RS total score at EOT will be ranked with any tied observations being assigned an average rank. The sum of the ranks for each treatment will be calculated. The non-parametric Wilcoxon rank-sum test will be utilised at a 2-sided 5% level of significance to test the null hypothesis that the distribution of post randomization CDM1-RS total score values for tideglusib and placebo is equal against the alternative hypothesis that the distribution of post-randomization CDM1-RS total score values for tideglusib and placebo are not equal. The Hodges-Lehmann estimate of the difference between the two treatments and 95% confidence interval will also be calculated.

Sensitivity analysis 7 – Multiple Imputation: MNAR control-based pattern

For this analysis, in-clinic and telehealth data will be used as for the primary analysis.

- Intermittent missing data for in-clinic visits will first be imputed using the FCS method, appropriate for non-monotonic missing data.
- Data missing after subjects discontinue the study early will be imputed using a regression, appropriate for monotone missingness. At each time point, missing data will be assumed to follow a distribution similar to scores for subjects who are still in the study and randomized to placebo.

The MI procedure will be employed as described for sensitivity analysis 1. The MMRM will be applied to the multiply imputed data sets, as described above for the primary estimand. The estimates from these models will then be combined using Ruben's (1987) rule and analysed to provide the endpoint estimates and summarized.

Sensitivity analysis 8 – Multiple Imputation: MNAR delta-adjustment pattern

For this analysis, in-clinic and telehealth data will be used as for the primary analysis.

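### The rank sensitivity analysis of the primary endpoint omits the baseline and age-group adjustment used in the primary model, and the adjusted non-parametric alternative is conditional and not specified as rank-based

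*SAP*

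**What the plan says.** All references are to SAP 6.13.1.1 unless stated.

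- **Primary model.** "The model will contain treatment, age group, visit and treatment by visit interaction as fixed effects, baseline CDM1-RS as a covariate". Age group is also the randomization stratification factor (SAP section 4; Protocol 7.1).
- **Sensitivity Analysis 6, variable.** "The change from baseline in CDM1-RS total score at EOT will be ranked with any tied observations being assigned an average rank".
- **Sensitivity Analysis 6, test.** "The non-parametric Wilcoxon rank-sum test will be utilised at a 2-sided 5% level of significance", with a Hodges-Lehmann estimate and 95% confidence interval. No covariate or stratum is named. The other seven sensitivity analyses all re-apply the primary MMRM, so this is the only one of the eight without its covariates.
- **Sensitivity Analysis 6, hypothesis.** The null is that "the distribution of post randomization CDM1-RS total score values for tideglusib and placebo is equal". That describes post-randomization scores, whereas the variable ranked is the change.
- **Adjusted non-parametric method.** Under the primary analysis, after residual plots: "Non-parametric analyses may additionally be performed if the data are found to be sufficiently non-normal". Then "This will include non-parametric analysis of covariance (ANCOVA") of change from baseline, "with treatment, baseline CDM1-RS and age group as covariates". No criterion for sufficient non-normality is given, and the text does not say that the method works on ranks.

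**The concern.** A rank analysis is normally included to show whether the primary result depends on approximate normality. Here it differs from the primary in further ways: the baseline covariate and age group are gone, and only EOT values are used. If it disagrees with the MMRM, the reader cannot attribute the disagreement to the shape of the distribution.

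Two consequences can be measured. Change tends to correlate negatively with the baseline score, so leaving baseline out as a covariate can cost precision. And a chance difference in baseline severity between two arms of about 25 children shifts the unadjusted comparison of change, while the adjusted primary largely corrects for it. The rank result could then appear to contradict the primary, or to flatter it, for a reason unrelated to normality. The analysis that would limit this is run only if someone judges the residual plots non-normal.

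**Working it through.** **Inputs from the documents.** Protocol 11.1 says that "the pooled standard deviation of change from baseline for the primary endpoint was 2.64". It gives a difference of 2.2 and 25 per group, with stated power of 82%. Protocol section 11 sets a two-sided 0.05 level.

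**Step 1: reproduce the stated power.** The noncentrality is 2.2 / (2.64 × √(2/25)) = 2.2 / 0.747 = 2.95 on 48 degrees of freedom. Power is 82.3% by the noncentral t (83.8% by the normal approximation). The protocol's 82% reproduces, and it is itself a calculation without covariates.

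**Step 2: what is assumed.** The documents give neither the baseline SD nor the baseline-to-EOT correlation ρ, so ρ is taken from 0.5 to 0.9 with equal variances at both times. Then:

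- baseline SD = 2.64 / √(2(1−ρ));
- share of change variance explained by baseline = (1−ρ)/2.

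| ρ | Baseline SD | Variance explained |
|---|---|---|
| 0.5 | 2.64 | 25% |
| 0.7 | 3.41 | 15% |
| 0.9 | 5.90 | 5% |

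**Step 3: power with baseline left to chance.** Simulation, 6,000 trials per setting, 25 per arm, scores rounded to whole points, roughly normal, complete cases. Rank ANCOVA means ranked change adjusted for ranked baseline; mean ANCOVA is a randomization-based ANCOVA on unranked change.

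| ρ | Wilcoxon | Rank ANCOVA | Mean ANCOVA |
|---|---|---|---|
| 0.5 | 79.6% | 88.3% | 90.0% |
| 0.7 | 78.4% | 83.5% | 85.6% |
| 0.9 | 78.7% | 79.2% | 80.4% |

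The cost of not adjusting, against rank ANCOVA, is 8.7, 5.1 and 0.5 points. Against mean ANCOVA it is 10.4, 7.2 and 1.7 points. Type I error was about 5% or below for every method.

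**Step 4: power with a fixed baseline imbalance.** An imbalance of 0.3 SD is assumed. The standard error of a baseline difference with 25 per arm is √(2/25) = 0.283 SD, so 0.3 SD is about 1.06 standard errors. Ignoring stratification, an imbalance at least that large in either direction arises in about 29% of trials. It shifts the unadjusted difference in change by (1−ρ) × 0.3 × baseline SD, which is 0.40, 0.31 and 0.18 points for ρ = 0.5, 0.7 and 0.9. Simulated power (3,000 trials per setting):

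| ρ | Tideglusib less severe at baseline: Wilcoxon / rank ANCOVA | Tideglusib more severe: Wilcoxon / rank ANCOVA |
|---|---|---|
| 0.5 | 63% / 86% | 93% / 88% |
| 0.7 | 67% / 82% | 90% / 84% |
| 0.9 | 73% / 80% | 86% / 81% |

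**Step 5: heavy-tailed errors.** Non-normality is the case for which a rank test is wanted, so the comparison was repeated with errors from a t distribution with 3 degrees of freedom scaled to the same variance (24 per arm, assumed baseline SD 3 to 6). Wilcoxon power was 91–94%, rank ANCOVA 95–96%, mean ANCOVA 84–90%. With normal errors in this setup, Wilcoxon gave 76–79% and rank ANCOVA 79–85%. An adjusted method on means can therefore fall below the plain Wilcoxon test when tails are heavy. An adjusted method on ranks did not.

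**The case against.** The strongest reply is that an unadjusted rank test with a Hodges-Lehmann estimate is a legitimate, assumption-light complement to an adjusted model. It holds its type I error under randomization, and its roughly 79% power is close to the covariate-free 82% on which the trial was planned. It is one of eight sensitivity analyses and gates nothing: SAP 6.14 ties the key secondary claim to the primary analysis only. All of this stands and limits the size of the point.

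It also stands that the conditional wording is firmer than it first looks. Once non-parametric analyses are triggered, the SAP says that the adjusted ANCOVA will be among them for CDM1-RS. But the trigger remains a judgement of plots without a criterion.

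A reader might infer three stronger things that the documents do not support:

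- **That Sensitivity Analysis 6 discards the baseline score.** It does not. The ranked variable is change, so baseline enters by subtraction; what is missing is its use as a covariate.
- **That the SAP already contains an adjusted rank method that only needs to be made mandatory.** The text names a non-parametric ANCOVA of change and does not say that it uses ranks. Step 5 shows why this matters: substituting a mean-based version for the Wilcoxon test could lower power in the setting where the rank analysis is most needed.
- **That adjustment would make the comparison with the primary a clean test of normality.** It would not. The MMRM uses all visits and handles missing data by likelihood, while any analysis of EOT change alone does neither.

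**Conclusion.** The point holds as a modest improvement. Sensitivity Analysis 6 leaves out the baseline covariate and age group that the primary includes. The loss in power runs from almost none (ρ = 0.9) to about 10 points (ρ = 0.5), and the documents do not allow that range to be narrowed. The more useful result concerns interpretation: a baseline imbalance of about one standard error can move the unadjusted test well below or above the adjusted ones. The mismatch between the variable ranked and the hypotheses stated is a separate wording error in the same paragraph.

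The figures rest on assumed correlations, equal variances at baseline and EOT, complete EOT data and an assumed 0.3 SD imbalance. Age group was not simulated because its cut-point is redacted. The primary analysis and its conclusion are unaffected.

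**What to change.** In SAP 6.13.1.1, Sensitivity Analysis 6:

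1. Add, unconditionally, a covariate-adjusted analysis of the ranked EOT change with treatment, ranked baseline CDM1-RS and age group, and state explicitly that it is performed on ranks.
2. Keep the Wilcoxon test and Hodges-Lehmann estimate beside it as the unadjusted supplement.
3. Reword the null and alternative hypotheses to refer to change from baseline in CDM1-RS total score at EOT.
4. State that both analyses use EOT values only, so that a difference from the MMRM is not read as evidence about normality alone.

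The cost is SAP wording and one more sensitivity table; no new data are needed. The 2024 SAP addendum, which documents post-hoc analyses, does not include this one. If it is run after unblinding, it should be reported next to the planned Wilcoxon result and labelled post hoc. The CGI-I section (SAP 6.13.2.1) pairs an unadjusted Wilcoxon test with an optional adjusted method in the same way and could be reviewed in the same edit; no calculation was made for it here.

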These analyses will use observed data from Visit (and baseline where change from baseline is calculated) and performed on the ITT set overall (i.e., without reference to treatment group.) In addition, for those subjects that achieve "minimal improvement" on the CGI-I at any visit, the change and percentage change from baseline in the CDM1-RS total score from the first such visit will be listed and summarised.

6.13.2 Clinical Global Impression-Improvement Scale (CGI-I)

The clinician administered Clinical Global Impression-Improvement (CGI-I) rating scale permits a global evaluation of the subject's improvement over time. The CGI-I requires the clinician to rate how much the subject's illness has changed (improved, worsened or stayed the same) relative to a baseline state via a seven-point Likert type scale which ranges from 1 = very much improved to 7 = very much worse.

The CGI-I is administered at Visits and and At Visits and III, the CGI-I will be rated twice for consistency evaluation purposes. One rating will be from an interview completed in-clinic and another from an interview completed via telehealth within the linear before the in-clinic visit.

The CGI-I at Visit is rated by the investigator against the subject's clinical presentation at Visit in period. For subsequent CGI-I ratings completed from Visit is nowards, the assessment is rated by the investigator against the subject's clinical presentation at Visit is rated by the investigator against the subject's clinical presentation at Visit is rated by the investigator against the subject's clinical presentation at Visit is rated by the investigator against the subject's clinical presentation at Visit is rated by the investigator against the subject's clinical presentation at Visit is rated by the investigator against the subject's clinical presentation at Visit is rated by the investigator against the subject's clinical presentation at Visit is rated by the investigator against the subject's clinical presentation at Visit is rated by the investigator against the subject's clinical presentation at Visit is rated by the investigator against the subject's clinical presentation at Visit is rated by the investigator against the subject's clinical presentation at Visit is rated by the investigator against the subject's clinical presentation at Visit is rated by the investigator against the subject's clinical presentation at Visit is rated by the investigator against the subject's clinical presentation at Visit is rated by the investigator against the subject's clinical presentation at Visit is rated by the investigator against the subject's clinical presentation at Visit is rated by the investigator against the subject's clinical presentation at Visit is rated by the investigator against the subject's clinical presentation at Visit is rated by the investigator against the subject is rated by the investigator against the su

The CGI-I may be assessed via telehealth instead of an in-clinic interview if required due to a COVID-19 related reason. The use of telehealth assessments is thought unlikely to be related to outcome, however, it will be assessed for balance between

the treatment groups and sensitivity analyses may be conducted in the event of imbalance.

6.13.2.1 Key Secondary Estimand and Supplementary Analyses

The estimand for the key secondary efficacy endpoint is the difference between treatments in the observed CGI-I score at EOT. Any data collected after study discontinuation will not contribute to the treatment effect estimation.

If a subject's in-clinic visit is unavailable, the data will be imputed with the corresponding telehealth assessment.

The null hypothesis being tested for the key secondary estimand is that there is no difference in CGI-I at EOT between the tideglusib and placebo treatment groups:

$$H_0$$
: $MeanCGI - I_{tideglusib} = MeanCGI - I_{placebo}$

The alternative hypothesis is that there is a difference in either direction in the CGI-I at EOT between the tideglusib and placebo treatment groups:

$$H_1$$
: $MeanCGI - I_{tideglusib} \neq MeanCGI - I_{placebo}$

The analysis will include data from Visit (randomisation) to Visit (EOT) inclusive. Data from other visits will be included in the summaries and listings.

Key Secondary Analysis

The key secondary estimand will be analysed using a MMRM.

The treatment difference between tideglusib and placebo at EOT will be estimated as the simple contrast in the treatment effect. The 2-sided 95% confidence interval (CI), based on the difference in the Least Squares (LS) means between the two treatment groups will be presented. The LS Means (and 95% CI) will additionally be presented for each treatment by Visit.

The MMRM model will be implemented using REML. The Kenward-Roger approximation will be used to estimate the denominator degrees of freedom and adjust standard errors.

Initially an unstructured covariance matrix will be investigated. If this analysis fails to converge, the following alternative structures will be tested in the following order until convergence is achieved: spatial spherical, spatial power, spatial Gaussian and compound symmetry. If a covariance matrix other than unstructured is selected, the estimated standard errors and variance-covariance matrix of the fixed-effects parameters will be computed using a robust "sandwich" estimator (*i.e.*, by specifying the EMPIRICAL option on the PROC MIXED statement).

The model will contain treatment, age group, visit and treatment by visit interaction as fixed effects, baseline CGI-I as a covariate.

If the baseline CGI-I and/or age group is not significant at the 15% level (i.e., p>=0.15) then a secondary analysis will be conducted with the term(s) removed from the model. Similarly if the p-value for the treatment by visit interaction is not significant at the 15% level, that term will be removed in the secondary analysis and the LS Means and treatment differences under the assumption of a constant treatment effect over time will be calculated.

Date:22FEB2023 Version: Final 2.0 ST/form/010/15 Normality of the data will be investigated through plots of the residuals. Non-parametric analyses may additionally be performed if the data are found to be sufficiently non-normal. This may include non-parametric ANCOVA (Koch G.G. et al, 1998 and Zink, R. and Koch, G.G., 2012) of the CGI-I at Visit with treatment, baseline CGI-I and age group as covariates. If the majority of subjects use three or fewer response categories, an approach suitable for categorical (binomial or multinomial) data may be used instead.

Any data collected after study discontinuation will not contribute to the treatment effect estimate. Only data up to study discontinuation will be used.

Missing Data

Missing data due to early study discontinuations or missed visits are assumed to be missing-at-random (MAR) and observed data only will be used for the primary analysis. The MMRM accounts for these missing data using a direct likelihood approach.

Sensitivity Analysis

Several sensitivity analyses will be applied to this endpoint:

Sensitivity analysis 1 - Multiple Imputation: MAR

At a visit, if a subject has no in-clinic or telehealth assessment data the visit is assumed to be MAR. This assumes that subjects with missing data follow the same trajectory as other subjects in their respective treatment arm that have complete data.

- Intermittent missing data will first be imputed using the MCMC method, appropriate for non-monotonic missing data.
- Data missing after subjects discontinue the study early will be imputed using a regression, appropriate for monotone missingness. At each time point, missing data will be assumed to follow a distribution similar to scores for subjects who are still in the study and randomized to the same treatment group.

The MI method (as described in Section 6.3) will be employed with the following assumptions/steps:

- Covariates that may be used in the MI will include treatment group and age group.
- 2. 20 imputations will be completed.
- 3. Seed number and covariates used for imputation will be agreed prior to data base lock and detailed in the TFL outputs.

The MMRM will be applied to each of the multiply imputed data sets, as described above for the key secondary estimand. The estimates from these models will then be combined using Ruben's (1987) rule and analysed to provide the endpoint estimates and summarized.

Sensitivity analysis 2 – Single Imputation: WOCF

At a visit, if a subject has no in-clinic or telehealth assessment data the visit is assumed to be MAR. This assumes that the trajectory of subjects who discontinue the study follows that of their worst observation. WOCF will be used and the MMRM as described for the key secondary estimand and applied to these data.

Sensitivity analysis 3 - Multiple Imputation: In-clinic visits only

At a visit, if a subject has a telehealth assessment and no in-clinic assessment, the visit is assumed to be MAR. Modelling in-clinic visits only (sensitivity analysis 3) is deemed a more valuable analysis than modelling telehealth visits only (sensitivity analysis 4).

- Intermittent missing data for in-clinic visits will first be imputed using the MCMC method, appropriate for non-monotonic missing data.
- Data missing after subjects discontinue the study early will be imputed using a regression, appropriate for monotone missingness. At each time point, missing data will be assumed to follow a distribution similar to scores for subjects who are still in the study and randomized to the same treatment group.

The MI procedure will be employed as described for sensitivity analysis 1. The MMRM will be applied to the multiply imputed data sets, as described for the key secondary estimand. The estimates from these models will then be combined using Ruben's (1987) rule and analysed to provide the endpoint estimates and summarized.

Sensitivity analysis 4 – Multiple Imputation: Telehealth visits only

At a visit, if a subject has an in-clinic assessment and no telehealth assessment, the visit is assumed to be MAR.

- Intermittent missing data for telehealth visits will first be imputed using the MCMC method, appropriate for non-monotonic missing data.
- Data missing after subjects discontinue the study early will be imputed using a regression, appropriate for monotone missingness. At each time point, missing data will be assumed to follow a distribution similar to scores for subjects who are still in the study and randomized to the same treatment group.

The MI procedure will be employed as described for sensitivity analysis. MMRM will be applied to the multiply imputed data sets, as described for the key secondary estimand. The estimates from these models will then be combined using Ruben's (1987) rule and analysed to provide the endpoint estimates and summarized

Sensitivity analysis 5 – Completers

The MMRM will be applied to all subjects who have completed the study to Visit

Sensitivity Analysis 6 - Rank Analysis

The CGI-I at EOT will be ranked with any tied observations being assigned an average rank. The sum of the ranks for each treatment will be calculated. The non-parametric Wilcoxon rank-sum test will be utilised at a 2-sided 5% level of significance to test the null hypothesis that the distribution of change from baseline for tideglusib and placebo are equal against the alternative hypothesis that the distribution of change from baseline for tideglusib and placebo are not equal. The Hodges-Lehmann estimate of the difference between the two treatments and 95% confidence interval will also be calculated.

Sensitivity analysis 7 – Multiple Imputation: MNAR control-based pattern

For this analysis, in-clinic and telehealth data will be used as for the primary analysis.

 Intermittent missing data for in-clinic visits will first be imputed using the FCS method, appropriate for non-monotonic missing data. Data missing after subjects discontinue the study early will be imputed using a regression, appropriate for monotone missingness. At each time point, missing data will be assumed to follow a distribution similar to scores for subjects who are still in the study and randomized to placebo.

The MI procedure will be employed as described for sensitivity analysis 1. The MMRM will be applied to the multiply imputed data sets, as described above for the primary estimand. The estimates from these models will then be combined using Ruben's (1987) rule and analysed to provide the endpoint estimates and summarized.

Sensitivity analysis 8 – Multiple Imputation: MNAR delta-adjustment pattern

This analysis will be done when there is a numerically positive treatment effect. For this analysis, in-clinic and telehealth data will be used as for the primary analysis.

- Intermittent missing data for in-clinic visits will first be imputed using the FCS method, appropriate for non-monotonic missing data.
- Data missing after subjects discontinue the study early will be imputed using a regression, appropriate for monotone missingness. At each time point, missing data will be assumed to follow a distribution similar to scores for subjects who are still in the study and randomized to the same treatment group. However, a fixed 5% worsening (delta-adjustment) to the outcome in the tideglusib group will then be applied.
- In the event of a statistically significant treatment effect, several deltaadjustments will be performed until non-significance occurs. This will be used to identify how much of a worse response would need to have occurred in the subjects with missing data in order to have overturned the significant result (a tipping-point analysis).

The MI procedure will be employed as described for sensitivity analysis. MMRM will be applied to the multiply imputed data sets, as described above for the primary estimand. The estimates from these models will then be combined using Ruben's (1987) rule and analysed to provide the endpoint estimates and summarized.

Supplementary Analysis

- The key secondary efficacy analysis will be repeated on the PPS and FAS.
- The proportion of subjects who improve, with CGI-I scores of 1-3 (Very much improved to minimally improved) vs. 4-7 (no change to very much worse) will be summarised and compared using a Fisher's Exact test.
- The proportion of subjects who worsen, with CGI-I scores of 5-7 (minimally worse to very much worse) vs. 1-4 (Very much improved to no change) will be summarised and compared using a Fisher's Exact test.
- The proportion of subjects with robust improvement, with CGI-I scores of 1-2 (Very much improved and much improved) vs. 3-7 (minimally improved to very much worse) will be summarised and compared using a Fisher's Exact test.
- Subgroup analyses will be performed by key baseline characteristics. The
 balance between treatment groups will be assessed and if any are evaluated
 as not being consistent a respective covariate will be included in the MMRM.
 For each subgroup, the main effect, treatment-by-subgroup interaction terms

and treatment by visit by subgroup interaction will be added to the model. Any interactions that are statistically significant at the 15% level for the end of treatment visit will have their nature described. These models will be used to estimate treatment comparisons within the subgroups that correspond with the sub-grouping factor. The results from the analysis are to be presented as described above in tables and/or figures. Subgroups of interest include but are not limited to:

- o Race (White, Non-White)
- Sex (Male, Female)
- o Age group (
- o Improvement in clinician-completed in-clinic CDM1-RS during the run-in period (Yes, No).

Summaries and Figures

Summary statistics of observed values will be presented as both continuous and categorical by visit and treatment for the in-clinic and telehealth visits separately.

By subject line plots of the observed CGI-I results will be presented over time by treatment group. In addition, line plots will present the adjusted LS means and associated SEs for the observed values over time, as estimated by the MMRM model, by treatment group.

For the 3 occasions in the study (Visit and and where dual telehealth and in-clinic assessments are conducted, summary statistics of the difference between the methods (in-clinic – telehealth) will be calculated and summarized using descriptive statistics over time. The intra-rater correlation will also be presented for each visit. A scatterplot for each visit will compare the observed value for the two methods for each subject, with in-clinic assessments being presented on the y-axis and telehealth on the x-axis. A linear regression line separately for each treatment will be included.

A line plot will present the observed values by visit, with in-clinic and telehealth assessments being presented on the same plot. Bar charts of the CGI-I frequency over time will be produced for the in-clinic and telehealth interviews separately. The CGI-I observed value (1 to 7) for Visits and will be presented on the x-axis and the number of subjects will be presented on the y-axis. The proportion of subjects achieving a CGI-I of 1, 2 or 3 will be presented similarly.

Data for in-clinic and telehealth assessments will be listed separately, with whether a telehealth assessment is within the pre-defined visit window for imputation as an inclinic assessment being annotated.

